## Measures and Data Collection

### Overview

Measurement will occur at baseline, 6 months (at the completion of the intervention), and 12 months after enrollment. Variables chosen for measurement are based on our conceptual framework (Section 3.4.1). At baseline, 6 months, and 12 months, patients (participants and peer mentors) will complete a written survey and assessments of A1c and blood pressure. Patients will receive \$25 for each assessment they complete. To understand features of successful vs. less successful peer partnerships, we will conduct semi-structured telephone interviews at 6 months of a purposive sample of participants and mentors in both study arms (choosing a sample with high rates of contact and a sample with low rates of contact). Using standard qualitative methods for identifying key themes in participant's experiences with this new program, we will identify central themes from these interviews associated with the success of the peer relationships and in meeting intervention goals. Participants and peer mentors in the peer mentor +iDecide arm will be asked about their experiences with iDecide and how use of the program affected their subsequent contacts and activities (e.g., setting and meeting 'action plan' goals, effectively raising questions and concerns with PCPs). Quantitative information about use of the IVR system will be collected via computerized records that the system maintains of all contacts with dates and time durations of all contacts as well as of attempted contacts. To assess peer mentors' experiences, we will conduct semi-structured interviews with a purposive sample of peer mentors with differing rates of participation (e.g., those who made regular contact with their assigned peers vs. those who did not).

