### 3.6.2 Description of Measures by Aim

**Aim 1:** Test the effectiveness of a technology-enhanced peer coaching (TEC) program in improving glucose control relative to peer support alone. At baseline, 6 months, and 12 months, a trained staff member will measure patients' A1c, using a Bayer DCA 2000+ analyzer, a portable analyzer producing A1c assays in approximately six minutes using finger stick blood samples. These assays have a test coefficient of variation (CV, measure of test precision) <5% as required by the National Diabetes Data Group and accurately measure A1c levels.[78] The DCA 2000 is reliable, easy to use, and much less burdensome to patients than venous blood draws. Our team has familiarity with the DCA 2000 from our prior studies.[40,56] To ensure quality control, venous A1c samples will be drawn from 5% of participants and analyzed at the Detroit VA's lab.

For our "usual care" observed group, we will use CDW data to measure A1c levels. More than 85% of diabetes patients who meet our eligibility criteria receive A1c testing at recommended intervals, which should ensure adequate numbers of patients with follow-up A1c levels in our control sample. For those with missing A1c data, we will use several approaches to examine possible biases (see section 3.7.5).

**Aim 2:** Assess the impact of the intervention on blood pressure and medication adherence as well as on key patient-centered outcomes, including patients' satisfaction and involvement with care, perceived social support, and diabetes-specific quality of life. These measures will be assessed at baseline, 6 months, and 12 months. We will measure blood pressure using an Omron® automatic blood pressure

monitor with memory and take the average of the two readings following American Heart Association guidelines. (Ideally we would also measure lipid levels, but have not found sufficiently reliable point-of-service machines for these measurements. At baseline we will collect information on most recent LDL, HDL, and total cholesterol levels from electronic medical records. If there are no recent values, the iDecide program text in that section will emphasize the importance of having these risk factor levels checked.) The baseline and 6-month surveys will take approximately 25 minutes to complete, and the 12-month survey will take approximately 15 minutes. Measures for the key patient-centered outcomes are:

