We will follow international guidelines for analysis and reporting of clinical trials.[97] In the first phase (data verification), we will examine the distribution of all study variables to assess extreme values, missing data, variances, possible coding errors, skewness, and type of distribution. We will examine baseline data for clinically important differences across the two study groups for potential prognostic indicators, such as patients' age, race, comorbidities, and baseline use of services. Although we do not anticipate any imbalances due to the randomization, any differences between experimental arms in baseline characteristics will be included as covariates in analyses comparing outcomes. In the second phase of our outcomes analyses, we will evaluate possible bivariate associations between patients' experimental condition and the outcomes, as well as between each covariate and the outcomes, prior to fitting multivariable models. This will be done to determine unadjusted measures of effect, assess possible confounders, and anticipate any collinearity in subsequent analyses. In the final phase we will fit multivariable models to identify main effects.

Analysis Plans by Aim

Aim 1: Test the effectiveness of a technology-enhanced peer coaching (TEC) program in improving glucose control relative to peer support alone. Our past experience in similar patient populations

suggests that the primary endpoint from the trial (change in A1c) will be close to normally distributed. To assess the primary endpoint for Specific Aim 1 (change in mean HbA1c from baseline to 6 months), we will use a general linear mixed regression model:

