where i represents the patient, I represents the intervention, j is the pair-group, β_l are parameters estimated from the data, X_{il} is the value of the l th fixed effect (peer support versus usual care) for the i th patient, β_j are parameters estimated from the data, Z_{ij} is the value of the j th random effect (pairs) for the i th patient, and ϵ_i is the residual error.[99] We anticipate that members of peer coach-peer partner pairs in both arms, because of their interactions with each other, might show a positive intraclass correlation (ICC), a component of the variance attributable to the group. As recommended for group-randomized trials, the mixed model analyses will thus address potentially inflated type I errors that could occur if such clustering were not taken into account.[97] If patients in either arm drop out of the study or request reassignment to another peer coach, they will be analyzed according to their initial pairing in an intent-to-treat analysis.

After unadjusted changes in A1c are determined, further analyses using mixed-model ANCOVA will adjust for confounding effects of any variables that differed substantially between treatment arms. Both unadjusted and adjusted means with 95% confidence intervals will be reported for both arms. While the primary endpoint is the mean difference between baseline and 6-month A1c concentrations, subsequent analyses will be conducted to determine whether the intervention additionally affects the difference between baseline and 12-month A1c (i.e., the sustainability of any treatment effects) using a repeated-measures mixed model ANCOVA.

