We will follow the same approach to comparing the observed usual care group with the peer support alone group. However, there is a higher likelihood of imbalances as the usual care group is observational, although they are drawn from the same eligibility pool as the participants. Therefore, we will include several key covariates in the analysis, including baseline A1c, age, gender, and race. We will also examine the data for differences in other potential prognostic indicators, such as baseline medication or service use, and include these variables in the regression if necessary. We will also need to examine whether biases may be caused by missing A1c data. Although the very high level of A1c testing in VHA is likely to lead to few missing data points, we will conduct sensitivity analyses using two approaches. In the first, we will assume that those with missing A1c levels at the end of the study had no improvement in their A1cs. In the second, we will use multiple imputation methods to fill in missing A1c values.

Aim 2: Assess the impact of the intervention on blood pressure and medication adherence as well as on key patient-centered outcomes, including patients' satisfaction and involvement with care, perceived social support, and diabetes-specific quality of life. For assessment of changes in systolic blood pressure and for the self-reported outcomes, we will use mixed effects models (similar to those in Aims 1) for

continuous outcomes, and generalized estimating equations (GEE) for ordinal outcomes with clustering.[98]

Aim 3: Identify patient characteristics associated with engagement in the intervention and mediators and moderators of the intervention's impact on patient outcomes. For these analyses, we will use multivariate modeling and path analyses.[99] Many of these outcomes will be measured using Likert scales. Thus, we will begin these analyses by developing contingency tables for ordered categorical data. We will then use generalized estimating equations (GEE), which are appropriate for modeling ordinal outcomes with correlated data.[99]

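### The Aim 1 primary model labels its fixed effect as peer support versus usual care, not TEC versus peer support alone, and its 'pairs' random effect does not match the mentor clusters used to size the trial

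*SAP*

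**What the plan says.** **Contrast.** Under Analysis Plans by Aim (SAP 3.7), Aim 1 is to "Test the effectiveness of a technology-enhanced peer coaching (TEC) program in improving glucose control relative to peer support alone". The general linear mixed model is introduced there for the primary endpoint, change in A1c from baseline to 6 months. The legend of that model then says that "X_{il} is the value of the l th fixed effect (peer support versus usual care) for the i th patient".

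The text after the legend expects correlation among "members of peer coach-peer partner pairs in both arms". The Protocol's Overview of measures likewise describes one arm as mentor plus the iDecide tool: "Participants and peer mentors in the peer mentor +iDecide arm will be asked about their experiences with iDecide".

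Usual care appears later in SAP 3.7 as a further, observational comparison with added covariates: "We will follow the same approach to comparing the observed usual care group with the peer support alone group". For that group, Protocol 3.6.2 says "we will use CDW data to measure A1c levels", whereas participants are tested on the study's portable analyser.

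**Cluster.** The legend says "j is the pair-group" and "Z_{ij} is the value of the j th random effect (pairs) for the i th patient". The sample-size text in SAP 3.7 equates pairs with coach–peer dyads and calls the ICC of 0.03 a within-pair value. The same paragraph counts mentors as the clusters: 148 patients and 37 mentors per group after attrition, with 348 patients and 87 mentors recruited.

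**The concern.** The legend is the only specification of the primary model in the available documents, and the one contrast it names is not the Aim 1 contrast. Patients in both randomised arms receive peer support, so an indicator of peer support versus usual care takes the same value for all 2 × 148 = 296 planned completers. It separates groups only once the observational usual-care patients are added. That would be a non-randomised comparison with A1c from a different source. The label also carries forward, since the usual-care comparison reuses the same approach and the Aim 2 models are described as similar to those for Aim 1.

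The cluster wording matters because the SAP relies on the mixed model to deal with inflated type I error. It does so if the random effect groups patients who share a mentor. It does not if the random effect is a dyad containing a single analysed patient: that intercept cannot be separated from residual error and carries none of the correlation between a mentor's patients.

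**Working it through.** **1. Contrast: the statements side by side**

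| Place | Contrast named or implied |
|---|---|
| SAP 3.7, sample size | Difference between the experimental groups |
| SAP 3.7, Aim 1 statement | TEC versus peer support alone |
| SAP 3.7, Aim 1 model legend | Peer support versus usual care |
| SAP 3.7, text after the legend | Coach–partner pairs exist in both arms |
| SAP 3.7, usual-care paragraph | Usual care versus peer support alone, observational, with covariates |

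Only the legend departs from the randomised contrast, and no other passage corrects it.

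**2. Which cluster the sizing used**

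Inputs (SAP 3.7, sample size): difference 0.5, SD 1.45, two-sided alpha 0.05, power 80%, ICC 0.03, 148 patients and 37 mentors per group.

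- Patients per mentor: 148/37 = 4, and 348/87 = 4. These are ratios of totals.
- N per group before clustering: 2 × (1.45 × (1.960 + 0.842)/0.5)² = 132.0 (normal); 133.0 using the t distribution.
- Design effect: DE = 1 + (m − 1) × 0.03.

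| Cluster | m | DE | N per group (normal / t) | In whole clusters |
|---|---|---|---|---|
| Pair | 2 | 1.03 | 136.0 / 137.0 | 136 / 138 |
| Four patients of one mentor | 4 | 1.09 | 143.9 / 145.0 | 144 / 148 |

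On the t-based figure, 145.0/4 = 36.2 rounds up to 37 mentors, and 37 × 4 = 148. The stated 148 patients and 37 mentors are therefore reproduced with the mentor as cluster. Pairs of two do not reproduce them.

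**3. What a literal one-patient dyad would cost**

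If correlation among a mentor's four patients is not modelled, true two-sided type I error = 2 × (1 − Φ(1.96/√(1 + 3 × ICC))).

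| Mentor-level ICC | Type I error |
|---|---|
| 0.01 (assumed) | 5.3% |
| 0.03 (plan's within-pair value, carried over) | 6.0% |
| 0.05 (assumed) | 6.8% |
| 0.10 (assumed) | 8.6% |

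At 0.03 the standard error is understated by 1 − 1/√1.09 = 4.2%.

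**4. Precision and power with the mentor as cluster, ICC 0.03**

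- SE with clustering: 1.45 × √(2 × 1.09/148) = 0.176. Ignoring it: 1.45 × √(2/148) = 0.169.
- 95% CI half-width: 1.96 × 0.176 = 0.345 (normal), or 0.351 (t, 72 df), against 0.330 if clustering is ignored.
- Power at 148 per group: Φ(0.5/0.176 − 1.96) = 81.1% (normal); 80.0% (t, 72 df).

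**The case against.** The best reply is that this is a slip nobody would act on. The sizing, the Aim 1 statement, the reference to pairs in both arms and the separate usual-care paragraph all fix the intended contrast. An analyst who coded the label literally in the randomised data would get a variable collinear with the intercept and notice at once. That stands: the matter is one of wording, not of design. It does not remove the need for correction, because the error sits in the definition of the primary analysis and other analyses refer back to that model.

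On clustering, the reply is that the documents largely point to the mentor. They call mentors the clusters, speak of variance attributable to the group, and analyse patients who change coach by their initial pairing. A dyad intercept with one analysed patient is also not a workable model. Much of this stands as well, so the finding is an ambiguity and not an error. The type I error figures apply only under the literal dyad reading; the plan does not say that it will ignore clustering.

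A reader might also infer that the sizing itself leaves the cluster open, because a mentor counted together with four patients (m = 5, DE 1.12) gives 132.0 × 1.12 = 147.9. The documents do not support that: 148/5 = 29.6 mentors, not 37.

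**Conclusion.** The contrast mismatch is certain on the text: the primary model's legend names a different comparison from the aim it serves. It should be corrected, but it changes no sample-size figure, since 148 per group already refers to the difference between the two experimental groups.

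A reader might infer that the primary model contains no term for TEC and so cannot estimate the Aim 1 effect. That goes beyond the documents. The displayed equation is not in the available text, the legend also assigns a symbol to the intervention, and the fixed effects are an indexed set. What can be said is that the only contrast the legend spells out is the wrong one.

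The cluster point is secondary and held with moderate confidence. The sizing uses mentors with four patients each, while the model's wording allows a dyad. Under the one-patient dyad reading, type I error would be about 6.0% instead of 5%. This rests on equal groups of four and on carrying the within-pair ICC of 0.03 over to patients sharing a mentor, which the documents do not establish.

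Nor do the documents settle whether mentors' own A1c values are analysed. The Protocol has them measured, and the sizing counts the 87 mentors apart from the 348 patients, but no passage says outright that they are excluded.

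**What to change.** In the Aim 1 model legend (SAP 3.7):

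1. Define the fixed effect as TEC versus peer support alone.
2. Define j and the random effect as a random intercept for the initially assigned peer mentor, matching the clusters used for sizing and the intent-to-treat rule on pairing.
3. State whether mentors' own A1c values enter the outcome.

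Give the usual-care comparison its own model statement, labelled peer support alone versus usual care. Apply the mentor intercept there only to peer-support patients, because the documents describe no mentor for usual-care patients.

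The cost is SAP wording and model code; N does not change. At ICC 0.03 the reported interval is slightly wider than if clustering were ignored (half-width about 0.345–0.35 against 0.33), and power at 148 per group remains 80–81%.

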Table 2 presents the measures we will use to assess factors we hypothesize may be associated with willingness to engage in the intervention (which may also be moderators) and mediators and

moderators of intervention effects as well as time points at which we will measure each of these. We include measures found to be significant mediators and moderators of effects in our P2P RCT.[40,84]

Mediators      Time Points\*      Original Source

Medication-taking Self-efficacy    1, 2      Perceived Competence Scale[85]

Autonomous Motivation      1, 2      Treatment Self-Regulation Questionnaire (TSRQ[85])

Medication adherence    1,2      Morisky Medication Adherence Measure[86]

Assessment of level and type of support received by Peer coach    2      Process measures used in P2P and by Robert Wood Johnson Foundation Diabetes Initiative [40]

Self-efficacy for shared decision-making with providers    1,2      Self-efficacy for Decision-making scale[87]

Medication doses and insulin starts      1,2      Survey items and electronic medical records

Moderators/Engagement Factors

Race    1      2010 US Census measures

Preferred and actual decision-making with providers    1      Preferred and Actual Participation in Decision-making Scales[88]

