We will use both quantitative and qualitative methods. We will compare patient characteristics and attitudes of participants and those not willing to participate in the study. For example, using VA administrative data, we will compare the characteristics of study participants (mean age, race, most recent A1C, co-morbidities) with those of diabetes patients treated in each site's outpatient clinics. Eligible refusals will be asked whether they would consent to a brief survey in which we will record information helpful in assessing the intervention's reach, such as diabetes distress, perceived need for support, interpersonal attachment styles, reasons for not enrolling, and existing sources of social support.

We will model independent associations and pathways linking intervention exposure to outcomes using nested multivariate regression. Subsequent nested models will introduce potential mediators, and we will evaluate changes in the magnitude of the relationship between experimental condition and outcomes before and after the covariates are introduced. Analyses of potential moderators will use standard approaches to evaluate potential interactions between these covariates and patients' experimental condition.[100] Independent variables and moderators will be centered before testing interactions, so that multicollinearity between first order and higher-order terms will be minimized. Statistically significant interactions will be interpreted by plotting regression lines for high and low values of the moderator variable. Stata routines greatly facilitate the plotting of these relationships.[101]

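### The non-randomised comparison of usual care with peer support alone has no planned covariate for willingness to take part and no sensitivity analysis for self-selection, so self-selection may be credited to peer support.

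*SAP*

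**What the plan says.** SAP 3.7, Aim 1, sets out the randomised comparison first and then turns to usual care: "We will follow the same approach to comparing the observed usual care group with the peer support alone group". It accepts that imbalance is more likely here, because "the usual care group is observational, although they are drawn from the same eligibility pool as the participants".

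The response has two tiers:
- **Always adjusted for:** "we will include several key covariates in the analysis, including baseline A1c, age, gender, and race".
- **Adjusted for conditionally:** "We will also examine the data for differences in other potential prognostic indicators, such as baseline medication or service use". Of these the SAP says it will "include these variables in the regression if necessary". It does not say what would make inclusion necessary.

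The same paragraph names two sensitivity analyses. One assumes no improvement where the final A1c is missing; the other uses multiple imputation. Both address missing A1c.

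Protocol 3.6.2 gives the outcome source for this group: "For our 'usual care' observed group, we will use CDW data to measure A1c levels". Under Aim 3 it introduces Table 2 as covering "factors we hypothesize may be associated with willingness to engage in the intervention (which may also be moderators". The list includes attachment style, perceived need for self-management support, and perceived benefits of and barriers to taking diabetes medication. SAP 3.7, Aim 3, adds that "Eligible refusals will be asked whether they would consent to a brief survey", for the purpose of assessing reach.

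**The concern.** Every patient in the peer-support arm agreed to take part. The available text does not say that the observed group was restricted to patients who would also have agreed. If willingness is related to A1c change under usual care, the two groups could differ at follow-up even if peer support does nothing. Adjustment for A1c, age, gender and race removes only the part of that difference that these four variables carry.

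The conditional tier does not close the gap. Medication and service use are at best indirect markers of willingness. Whether they enter is also decided after the data have been inspected. SAP 3.7 (approach to all analyses) looks at unadjusted associations with outcome before any multivariable model is fitted, so that order of work would allow the choice to be made with the unadjusted difference already known.

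The stake is interpretive. In the available text this is the only contrast that bears on whether peer support alone changes A1c. If TEC and peer support turn out alike, readers will look to it to judge whether both helped or neither did.

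**Working it through.** **1. The plan's own figure.** SAP 3.7 gives a difference of 0.5, SD 1.45, two-sided alpha 0.05, power 80%, ICC 0.03, and 148 patients with 37 mentors per group.
- Without clustering: n = 2 × [1.45 × (1.960 + 0.842) / 0.5]² = 132.02 per group.
- With four patients per mentor (148/37 = 4), the design effect is 1 + 3 × 0.03 = 1.09, and n = 143.9, so 144.
- With five per cluster (mentor included), the design effect is 1 + 4 × 0.03 = 1.12, and n = 147.9, so 148 as stated.
- Attrition: 148 / 0.85 = 174.1, against 174 stated.

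The figure reproduces, but it sizes the randomised comparison. The available text gives no size for the usual-care group.

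**2. What is measured, and what reaches the usual-care model.**

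| Item | Where it appears | Role in the usual-care model |
|---|---|---|
| Baseline A1c, age, gender, race | SAP 3.7, Aim 1 | Always included |
| Medication or service use, other indicators | SAP 3.7, Aim 1 | Conditional, no criterion |
| Attachment style, perceived need, medication benefits and barriers | Protocol 3.6.2, Table 2 | None stated |
| Refuser survey (distress, perceived need, attachment, reasons) | SAP 3.7, Aim 3 | None stated; used for reach |
| Propensity strata | SAP 3.7.5 | Model the chance of having outcome data, not of enrolling |

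No row supplies a covariate for willingness, and no row tests for confounding by it.

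**3. What a given residual bias would do (illustration).** Assumptions: no true effect; SD 1.45; 148 in peer support with design effect 1.09; usual care unclustered, with 148 or 1,000 patients. Let b be the bias left after adjustment.
- SE = 1.45 × √(1.09/148 + 1/148) = 0.172 with 148 usual-care patients.
- SE = 1.45 × √(1.09/148 + 1/1000) = 0.133 with 1,000.
- P(significant) = P(Z > 1.96 − b/SE) + P(Z < −1.96 − b/SE).

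| b (A1c points) | 148 in usual care | 1,000 in usual care |
|---|---|---|
| 0 | 5.0% | 5.0% |
| 0.1 | 8.9% | 11.7% |
| 0.2 | 21.3% | 32.6% |
| 0.3 | 41.3% | 61.9% |

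A larger usual-care group makes a biased answer look more certain.

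**4. The opposite sign.** The formula depends only on true effect plus bias. With 148 per group, a true difference of 0.5 and no bias is detected with probability 82.7%. With a bias of 0.2 against peer support the net shift is 0.5 − 0.2 = 0.3, and the probability falls to 41.3%.

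**5. Would separating refusers settle it?** Assume that willing patients improve d = 0.2 to 0.4 points more than unwilling ones under usual care, and that a share w = 30% to 70% of never-approached patients would have been willing. The expected gap between never-approached patients and refusers is d × w, from 0.2 × 0.3 = 0.06 to 0.4 × 0.7 = 0.28. With 148 split 74/74 (assumed), SE = 1.45 × √(2/74) = 0.238 and power is about 6% to 22%. A null result would reassure little.

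**6. Precision of a negative control.** Assume the same SD for change before enrolment, when no mentor clustering exists, and 148 per group. Then SE = 1.45 × √(2/148) = 0.169, and the 95% CI is about ± 1.96 × 0.169 = ± 0.33. The interval is informative about the range of bias, but a non-significant result is not proof of none.

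**The case against.** The SAP labels this group observational, concedes the risk of imbalance, adjusts for baseline A1c and leaves room for more. The comparison is secondary to a randomised one. All of that stands, and it limits the weight of the point.

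Several stronger readings are tempting, and the documents do not support them:
- **That adjustment is confined to four variables.** The list is introduced as open-ended, and the next sentence provides for further prognostic indicators. The weakness is that those additions are conditional, with no criterion.
- **That the observed group is made up of people who did not enrol, or is rich in refusers.** The text says only that it comes from the same eligibility pool. Refusers, never-approached patients or both would fit, and the defining text may lie outside what is available.
- **That the Protocol says the willingness factors drive A1c.** It hypothesises that they may relate to engagement and may moderate the intervention's effect. Neither is a claim that they predict A1c change under usual care, which is what confounding requires. The SAP also uses engagement for contact frequency and duration among enrolled dyads.
- **That nothing in the plan could show who joins.** Under Aim 3, participants are compared with clinic patients on administrative data, and consenting refusers are surveyed. This would show whether participants differ, although it is not carried into the A1c model.
- **That the bias must favour peer support.** Patients who join because they feel greater need could do worse.

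**Conclusion.** The point holds as a limited one. The usual-care comparison always adjusts for four named variables and adds others by an undefined rule after the data have been inspected. It includes no measure of willingness to take part, and its sensitivity analyses concern missing A1c only. Self-selection may remain and be credited to peer support.

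The size and direction of the bias cannot be derived from the documents. The probabilities of 8.9% to 41.3% rest on assumed biases of 0.1 to 0.3 points remaining after adjustment, an assumed 148 usual-care patients, the SAP's SD and ICC, and no true effect. They show how sensitive the comparison is, not how large the bias will be.

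The randomised comparison of TEC with peer support alone does not depend on this contrast. A reader should not infer that the primary result is compromised.

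**What to change.** In the usual-care paragraph of SAP 3.7, Aim 1:

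1. Replace the conditional rule with a covariate set fixed in advance and used whatever imbalance is observed. Draw it from VA records available for both groups: baseline A1c, age, gender, race, baseline glucose-lowering regimen, prior-year service use, co-morbidities, and prior A1c where available.
2. Add a negative-control sensitivity analysis. Fit the same model to CDW A1c change over a period before enrolment, when peer support cannot have acted. Shift the covariate window back so that no covariate overlaps the outcome. Report the estimate with its 95% CI beside the main contrast, and do not use a significance threshold as a pass mark.
3. Describe the contrast as an observational association, not as an effect of peer support.
4. If recruitment status is recorded, report refusers against never-approached patients as a descriptive sensitivity analysis only, given its low power. Never-approached patients would still be a mix of willing and unwilling.

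The cost is SAP wording, a few more CDW fields, and the loss of some patients without earlier A1c values from the negative control.

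The negative control has a limit. Protocol 3.6.2 measures enrolled patients with a study finger-stick analyser and the observed group from CDW. An analysis that takes A1c from CDW for both groups cannot detect bias from that difference, which needs separate attention.

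### The Aim 3 administrative comparison of participants with the unwilling uses clinic diabetes patients not limited to the eligible, so it mixes entry criteria and being approached with willingness

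*SAP*

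**What the plan says.** The Aim 3 text in SAP section 3.7 states the purpose first: "We will compare patient characteristics and attitudes of participants and those not willing to participate in the study". The next sentence gives an example. Using VA administrative data, it compares participants on "mean age, race, most recent A1C, co-morbidities) with those of diabetes patients treated in each site's outpatient clinics". The comparator is described only as patients seen in the clinics.

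A second component follows: "Eligible refusals will be asked whether they would consent to a brief survey in which we will record information helpful in assessing the intervention's reach". Its content is introduced as examples, "such as diabetes distress, perceived need for support, interpersonal attachment styles, reasons for not enrolling, and existing sources of social support".

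Elsewhere the plan shows that entry criteria exist and that an eligible group has been identified. Protocol section 3.6.2 states: "More than 85% of diabetes patients who meet our eligibility criteria receive A1c testing at recommended intervals". In the Aim 1 analysis, the SAP says of usual-care patients: "although they are drawn from the same eligibility pool as the participants". The Protocol takes their A1c from CDW data.

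**The concern.** The question concerns willingness, which is defined only for patients who could have joined and were asked. The clinic comparator is not restricted in either way. It may include patients who fail the entry criteria, eligible patients nobody contacted, and the participants themselves. Participants were selected by the criteria before willingness played any part.

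At stake is the interpretation of one part of Aim 3. A report could say that patients with higher A1c, or of a certain age, were more ready to join, when some or all of the difference came from the entry rules or from who was invited. Willingness is a stated interest of this aim. Protocol Table 2 is introduced as covering factors that may relate to it, and race, one of the four administrative variables, appears there among the moderators and engagement factors.

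**Working it through.** The plan gives no sample size, effect or test for this comparison, so there is no figure to reproduce. The check is of the comparator.

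**1. What the contrast contains.** For any variable, let P, C, E and A be its means in participants, clinic diabetes patients, eligible patients, and eligible patients who were approached. Then

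P − C = (E − C) + (A − E) + (P − A).

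- E − C is the effect of the entry criteria. It is zero if the variable is unrelated to them.
- A − E is the effect of who was approached. It is zero if the variable is unrelated to that.
- P − A is the only term that reflects agreeing to take part.

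The example in the SAP estimates the sum and cannot separate the terms.

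**2. Participants inside the comparator.** If participants form a share p of the clinic group and N is the mean in everyone else, then C = pP + (1 − p)N, so P − C = (1 − p)(P − N). Leaving participants in shrinks the difference by the factor 1 − p. Clinic size is not given, so p is unknown. If the clinics are large, this effect is small.

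**3. Whether the refuser survey closes the gap.** It is confined to eligible refusers, so the entry-criteria term does not arise for the topics it covers. It needs a refuser's consent, and its named topics are psychosocial. Age, race, A1c and co-morbidities are not among them, although the list is open-ended. The only stated comparison on those four variables is therefore the one with clinic patients.

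**4. Illustration of the first term, on assumed inputs.** The documents give no clinic A1c mean or SD, and the available text does not show whether there is an A1c entry threshold. Assume a normal clinic distribution with mean μ and SD s, a minimum-A1c threshold c, and willingness and approach both unrelated to A1c. Then

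P − C = s·φ(a)/(1 − Φ(a)), with a = (c − μ)/s.

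For μ = 7.5, s = 1.2, c = 7.0: a = −0.417 and 1.2 × 0.366/0.662 = 0.66.

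For μ = 7.2, s = 1.5, c = 8.0: a = 0.533 and 1.5 × 0.346/0.297 = 1.75.

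| μ, s (assumed) | c = 7.0 | c = 7.5 | c = 8.0 |
|---|---|---|---|
| 7.2, 1.2 | 0.83 | 1.16 | 1.52 |
| 7.2, 1.5 | 1.07 | 1.39 | 1.75 |
| 7.5, 1.2 | 0.66 | 0.96 | 1.30 |
| 7.5, 1.5 | 0.90 | 1.20 | 1.53 |

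Under the same assumptions, the expected difference from eligible non-participants is 0. With no criterion bearing on A1c, the difference from clinic patients is also 0. The table shows that the mechanism can produce a visible gap. It does not estimate the gap in this trial.

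**The case against.** The strongest reply is that the clinic comparison is offered only as an example, under a sentence that already commits to the right contrast, and that the next sentence surveys eligible refusers and asks why they did not enrol. Comparing participants with the clinic population is also a standard way to describe representativeness, and the SAP does not say that it would read a difference as willingness.

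Much of this stands. The survey is a real second component, and a whole-clinic comparison is legitimate under its proper label. What remains is that the example is the only stated comparison on the four administrative variables, it is introduced as an instance of comparing participants with the unwilling, and its comparator is a different group.

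A reader might go further in three ways that the documents do not support.

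- **That the comparison measures the entry criteria instead of willingness.** It mixes them. How much the criteria contribute cannot be judged without seeing them.
- **That the gap can be sized, for example as a multiple of the 0.5-point A1c effect in the sample size calculation.** The clinic distribution and threshold above are assumed. The 0.5 is a between-arm difference, sized with the SD of A1c decline; a cross-sectional gap between two groups of patients is a different quantity.
- **That Aim 3 as a whole would be answered wrongly.** The SAP grades engagement by the frequency and duration of recorded calls and relates it to baseline factors. That analysis and the mediator and moderator models do not use this comparator.

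**Conclusion.** The point holds as a mismatch between a stated question and the comparator chosen to illustrate it. Followed as written, differences in age, race, most recent A1c or co-morbidities could not be attributed to willingness, because eligibility and being approached are confounded with it. The refuser survey only partly fills the gap.

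The size is undetermined. It is zero for a variable unrelated to both the criteria and the approach process. For A1c, the illustrative range of 0.66 to 1.75 points depends wholly on the assumed mean, SD, threshold and normal shape. The conclusion about the comparator needs none of those inputs. It needs only that the clinic group is not restricted to eligible patients, which is how the text reads.

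This is a secondary, descriptive analysis, and the primary A1c comparison between arms is unaffected. It is a cheap improvement.

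**What to change.** In the Aim 3 text of SAP section 3.7, change the administrative-data comparator to non-participants in the eligibility pool that already supplies the usual-care group, and state that participants are excluded from it. Where recruitment records and data permissions allow, show two columns: eligible patients who were approached and declined, and eligible patients who were not approached. The first column bears on willingness; the second shows whether those approached differ from the rest of the pool. If the two cannot be separated, say that the contrast still combines approach with willingness.

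If the whole-clinic comparison is kept, label it as a description of how representative participants are of clinic patients, and do not interpret it as evidence on willingness.

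The cost is a change of SAP wording, a smaller comparator, and some work to link recruitment records to administrative data. The available text does not show whether such records exist for decliners or whether their use is permitted, so the split is conditional. Restricting the comparator to the eligibility pool does not depend on it.
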